F. Data Collection and Measures

Data for primary and secondary aims will be collected by study staff from patient surveys, organizational surveys, and provider logs. The assessment package previously developed and implemented by study investigators (R34 MH74509, R01 MH79994) was informed by the RE-AIM framework for evaluating implementation of EBPs. Key measures include patient-level outcomes, LG uptake and fidelity, organizational factors, and REP, EF, and IF activities (Table 3). Data sources include patient-level (surveys), site-level (provider surveys), and project staff logs.

Patient data: Lists of patients and contact information that were identified by the LG providers during the first 3 months of REP (pre-randomization) will be sent to study outcomes assessors who will conduct phone surveys at baseline (after the REP provider training is complete), and 6, 12, 18, and 24 months later. Patient baseline assessments will include assessments already used

in routine clinical care and will be conducted by project staff by phone after the LG provider identifies eligible patients but before the first LG sessions are implemented. Once project staff receive patient lists, they will contact patients, describe the purpose of the study, and ask if the patients would like to participate. Patients will be compensated \$10 for completing each assessment. Patient-level data will be coded with a unique identifier. There will be a crosswalk file that is password protected that is only available to be accessed by study staff that will link unique study ID with a link to the person's identity.

Table 3: Primary and Secondary Assessments – Baseline and Follow-ups

Aims	Measure	Source
1a. Primary outcomes	Health-related quality of life-SF-12 mental health score	Patient survey
1b. Secondary outcomes	Functional impairment-WHO-DAS	Patient survey
	Psychiatric symptoms-PHQ-9, GAD-7, ISS	Patient survey
	LG fidelity and uptake (# sessions, contacts)	LG provider logs, patient surveys
Secondary aims	LG implementation costs (patient, site perspective)	Patient survey, chart review, logs
	REP costs	Study staff logs
	Facilitation costs	Staff, LG provider, Facilitator logs
Covariates	Patient demographic, clinical factors, behaviors use	Patient survey, chart review, logs
	Organizational factors (OTM, ORCA, EBPAS)	Site leader, provider surveys

Patient outcomes will be ascertained from a brief, previously established survey used in routine care settings that includes health-related quality of life (the primary outcome, SF-12), functional impairment (World Health Organization Disability Assessment Scale- WHO-DAS), and mental health symptoms (secondary outcomes), including the PHQ-9, GAD-7 for anxiety symptoms, and the Internal State Scale for manic symptoms. Additional questions on LG use will also be included to provide confirmatory information on LG fidelity and uptake (see description of LG fidelity measures below).

Patient demographic, clinical, and use data will be ascertained from the survey including race/ethnicity, age, marital status, education, employment status, social support, incarceration history, homelessness, adherence, and substance use. Utilization, including inpatient, outpatient, as well as data on medical and psychiatric comorbidities will be ascertained from the patient assessment.

Provider surveys: Provider surveys will be used to ascertain information on organizational factors. These organizational surveys will be used to inform activities designed to implement promising ways to improve clinical care and health care operations. The site clinical leader or administrator as well as the LG provider and the IF from sites randomized to the **REP+EF/IF** will complete surveys on organizational factors that might impact implementation and outcomes, and inform the identification of more or less responsive sites for future adaptive implementation work. First, site leaders will be contacted prior to the initiation of the REP in-service to complete an organizational survey previously developed by study investigators (with a >90% completion rate) at the beginning of the study. This survey is used to determine organizational characteristics that might potentially explain variation in EBP uptake, including resources, staff turnover, and degree of integrated primary and mental health care.

Additional organizational factors based on surveys completed by the site clinical leaders, LG provider and IFs will be assessed prior to the initiation of REP, then again at 12 and 24 months later to assess changes in organizational features that are potentially impacted by REP and Facilitation.

LG fidelity: Because this study is designed to assess real-world implementation of routine clinical care, minimally invasive measures developed by study investigators will be used to assess use of LG services. LG providers will complete a computerized log of LG encounters, which will

ascertain the number of completed group sessions and provider follow-up contacts received by each patient. LG fidelity will also be assessed using a previously established measure that combines information from the LG provider logs with confirmatory information from patient surveys. The fidelity monitor calculates a total score based on number of group sessions (0-4) and follow-up contacts (0-6) completed by each patient. Average patient completion of group sessions of $\geq 75\%$ was associated with improved mental health-related quality of life.

Table 4: Recording Time Spent on REP, Facilitation, and LG

REP (all sites)
LG provider and site representative time spent at in-service, training
LG provider time spent with LG trainer on phone follow-ups, documentation
Project staff (investigators, personnel): Packaging LG, training, site contacts, note-taking
EF (REP+EF sites)
LG provider time spent with External Facilitators (phone contacts, email follow-ups)
LG provider actions taken to facilitate LG, documentation
Project staff (EF): Time spent with provider contacts, follow-up technical assistance, documentation of goals with each site
IF (REP+EF/IF sites)
Time IF spent with EF, LG providers in meetings and establishing goals, site priorities, develop rapport
Time IF spent working out LG barriers, strategizing and aligning LG goals with site goals
Time IF spends with EF and LG provider in summarizing implementation progress with leadership, business plan development
LG Implementation (all sites)
Group sessions: Number of outpatient clinic visits w/ LG patients actually completed
Follow-up contacts: Time spent on each contact
Other Face-Time: Any time spent seeing LG patients face-to-face or on phone outside of sessions/contacts
Phone Time: Any time spent on the phone only with LG patients. Include time spent leaving messages, playing "phone tag", etc.
Care Coordination: Any and all time spent on behalf of a LG patient when patient is not present (e.g., phone, consultation)
Charting Time: Any time spent charting for a LG patient (e.g., registry, progress notes, updating treatment plans, etc.)

Implementation Strategy (REP, EF/IF) Use and Costs (Table 4): Personnel time is likely to account for the vast majority of costs associated with REP and Facilitation. All activities involving REP, EF, and IF will be documented using previously established log forms (e.g., R01 MH 79994) and all costs will be multiplied by personnel wage rates including fringe. We will estimate time costs incurred by both site employees as well as project staff (REP trainer, Facilitators). We chose to focus on a cost analysis from the perspective of the sites because the added cost of paying for and providing Internal Facilitation will be the major concern of these stakeholders, who are the target audience for potentially spreading value-based implementation frameworks

REP Costs from the site's perspective: We will estimate the costs of the REP implementation from the site's perspective by collecting information on the total time LG providers spent on 1) in-services, 2) training, and 3) monitoring by surveying the providers involved in each step based on the LG registry log.

REP and External Facilitation costs: Total costs of REP and EF implementation will be estimated based on study staff logs by summing up the total time spent by the study staff in LG package dissemination, in-services, training, and follow-up site calls and documentation.

Internal Facilitation Costs: IF costs are primarily borne by the site and are detailed in Table 4. Each IF will complete a log of activities using similar procedures in ROCC. The total time spent in IF activities will be multiplied by personnel wage rates.

LG Costs from the site's perspective will also be estimated for each site. Study staff will ascertain information from the LG provider registry on number and time for each group session, follow-up contact, as well as for additional provider and patient encounters and clinical documentation

(Table 4).

VI. Analyses and Evaluation

Intent-to-treat. Every effort will be made to collect patient level outcomes across all 80 sites and patients (N=1600) to conduct the primary and exploratory analyses (see below). The 40 sites randomized at month 6 (total 800 patients) will be included in the intent-to-treat randomized sample. The Primary Aim analysis will compare strategies in non-responding sites (k=40) beginning with **REP+EF/IF** versus strategies beginning with **REP+EF** on longitudinal change in patient-level SF-12 mental health scores (MCS- primary outcome). This analysis is a comparison of cells A+B+C vs. D+E (Figure 2). For this analysis, the longitudinal outcome is SF-12 mental health scores measured at Months 6 (pre-randomization), 12, 18, and 24. The primary contrast is the between groups difference in change from Month 6 to Month 18. The follow-up contrast at Month 24 will also be examined in this and all subsequent analyses. Linear mixed models (LMM), also known as random effects models, fit with SAS PROC MIXED will be used to analyze the longitudinal data. LMMs use all available measurements, allowing subjects to have an unequal number of longitudinal observations and producing unbiased parameter estimates as long as unobserved values are missing at random. The analysis will fit a 3-level (repeated measures for each person clustered within site) LMM with fixed effects for the intercept, time, group, and a group-by-time interaction term, where group is an indicator of **REP+EF/IF** vs. **REP+EF**. The LMM will also include random effects for site and time, an unstructured within-person correlation structure for the residual errors, and it will adjust for the following pre-randomization measures collected through Month 6: state and type of practice (primary care- or mental health site). Model diagnostics will be used to determine the suitability of more parsimonious (e.g., autoregressive) correlation structures, and nonlinear (e.g., piecewise linear or quadratic) effects for time. LMMs similar to the above for the primary outcome will be conducted for the secondary outcomes: **REP+EF/IF** vs. **REP+EF** on change in number of LG encounters, functional impairment, and psychiatric symptoms.

The goal of the Secondary Aim 1 analysis is to determine whether continuing **REP+EF** versus augmenting with **REP+EF/IF** leads to changes in outcomes, among sites who are non-responsive at Month 12. This analysis is a comparison of cells B vs. C (Figure 2). Both primary and secondary longitudinal outcomes above will be examined using an LMM similar to that described above, except (a) including only the subset of sites that do not respond at Month 12 to **REP+EF**, (b) using monthly longitudinal outcomes from Month 12 to Month 24, and (c) the LMM will use dummy-indicators for time (i.e., time-saturated model since there are only 3 measurement times for each longitudinal outcome).

The Secondary Aim 2 analysis will involve an analysis of implementation costs. The implementation (REP, EF, IF) costs will be summed for each site as a measure of total costs and changes in costs will also be assessed over time (6, 12, 18, 24 months). An exploratory analysis of the incremental effectiveness of IF by comparing costs from sites given **REP+EF/IF** versus those with **REP+EF** will be conducted from the site's perspective. In regression models of costs, Generalized Linear Models with log link functions will be used to correct for heteroscedasticity and reduce the impact of outliers. Effectiveness will be measured by changes in health utilities using the SF-6 (a subset of SF-12 questions) as well as the Euro-QOL 5D. Cost-effectiveness will be calculated as the ratio of incremental average site-level cost and incremental average effectiveness (change in patient-level utilities) of IF. A standard nonparametric bootstrapping approach will be used to calculate confidence intervals and cost-effectiveness acceptability curves.

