
The overarching goal of this study is to build the most cost-effective adaptive implementation strategy involving REP and Facilitation to enhance the update of an EBP for mood disorder and subsequent changes in patient outcomes using clinical assessments available in routine care. The EBP, Life Goals (LG), is an evidence-based psychosocial treatment shown to improve outcomes among patients with mood disorders and will be implemented as part of routine clinical care at each organization. In this study, sites initially receiving REP that have not fully implemented LG (e.g., <10 patients receive the LG EBP) will be randomized to receive additional External Facilitation (**REP+EF**) or External plus Internal Facilitation (**REP+EF/IF**). At 12 months, sites that are non-responsive to External Facilitation (**REP+EF**) will be re-randomized to receive **REP+EF** or **REP+EF/IF** and then followed for another 12 months to determine whether longer-term exposure to Facilitation is needed. Because sites and not patients will be randomized, the EBP (LG) is already an established evidence-based clinical practice that will be implemented as part of routine clinical care, and because all sites will receive some additional state-of-the-art

implementation support through Facilitation, this project involves health care operations improvement within select healthcare systems.

Primary Study Aim. To determine whether sites that do not exhibit response to REP alone after 6 months (e.g., <10 patients receiving LG), the effect of adding an External and Internal Facilitator (**REP+EF/IF**) versus adding an External Facilitator alone (**REP+EF**) on use of the EBP (LG) and changes in routinely collected patient clinical assessments (health-related related quality of life and mood symptoms).

Secondary Aim 2. To estimate the costs of REP+EF/IF compared to REP+EF at the sites.

Secondary Aim 3. To describe the implementation of EF and EF/IF, including interaction between the two roles and the specific strategies EFs and IFs use to facilitate LG uptake across different sites.

Results from the project will be used to inform activities designed to implement promising ways to improve clinical care and healthcare operations.

III. Background and Significance

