C. Study Design flow. Primary care or mental health outpatient clinics agreeing to participate will be randomly selected (N=80 total) and initially offered REP for six months in order to implement LG. Based on previous research and preliminary data, it is expected that after six months of REP at least two-thirds of sites will be non-responsive to REP. The primary focus of the randomized comparisons in this study are sites that are initially non-responsive to REP (k=40), defined based on our preliminary studies as <10 patients receiving LG within six months of initiating REP and that patients received <75% group sessions. (Although not part of the primary randomized comparisons, sites that are responsive at 6 Months will continue to be followed and outcomes will be assessed). The non-responsive sites will be randomized 1:1 to receive additional External Facilitation (**REP+EF**) or External plus Internal Facilitation (**REP+EF/IF**). After another six months (at Month 12), sites that are still non-responsive (based on the same criteria) will be randomized 1:1 to either continue **REP+EF** or augmentation with IF (**REP+EF/IF**). All sites are followed for a total of 24 months. Patient-level outcomes will be assessed by study staff using assessments considered part of routine clinical care (e.g., symptoms and quality of life) starting at the initiation of REP and then at 6, 12, 18, and 24 months later among a pre-selected cohort of n=20 patients per site who are identified by site providers for LG (total patients participating in the project N=k*n=800). Patients receiving Life Goals as part of their routine clinical care may opt in or out in participating in the outcomes assessment component. As with our prior implementation work (R01 MH79994), independent evaluators (study staff who are not aware of the assignment to **REP+EF** or **REP+EF/IF**) will conduct study outcomes assessments to ensure consistency of

data collected across sites and to prohibit provider/site or investigator assessment bias. Pre-identification of LG recipients also maximizes consistency of the patient population across sites (see patient criteria below).

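### The goal is the most cost-effective adaptive strategy, but neither strategy that starts with REP+EF is compared with immediate REP+EF/IF, on outcome or on cost

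*Combined protocol and SAP*

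**What the plan says.** Section II (Project Aims) gives the purpose: "The overarching goal of this study is to build the most cost-effective adaptive implementation strategy involving REP and Facilitation". Its Primary Study Aim is narrower: among sites not responding to REP, the effect of adding EF/IF rather than EF alone.

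The design has two randomizations:

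- **Month 6** (Section V.C): "The non-responsive sites will be randomized 1:1 to receive additional External Facilitation" or External plus Internal Facilitation.
- **Month 12** (Section V.C): "sites that are still non-responsive (based on the same criteria) will be randomized 1:1 to either continue" REP+EF or have IF added. Sections II and V.D restrict this step to the REP+EF arm; Section II describes them as "sites that are non-responsive to External Facilitation".

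Section VI then plans three comparisons:

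- **Primary analysis**, SF-12 MCS: "This analysis is a comparison of cells A+B+C vs. D+E". On timing: "The primary contrast is the between groups difference in change from Month 6 to Month 18". Month 24 is a follow-up contrast.
- **Secondary Aim 1**: B against C, among REP+EF sites still non-responsive at Month 12.
- **Secondary Aim 2**: costs, with an exploratory cost-effectiveness ratio for IF, comparing REP+EF/IF sites with REP+EF sites. It does not say where cell C belongs, although those sites receive EF alone and then EF/IF.

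No weighted analysis is described, and neither A+B nor A+C is set separately against D+E.

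**The concern.** Section II justifies the adaptive approach by noting that IF takes site time and that some sites may not need it. Section V.F adds that the cost of IF is what sites will care about most. The practical question is therefore whether reserving IF for sites that fail on EF gives up anything compared with giving IF to every REP non-responder at Month 6. That is A+C against D+E.

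No planned comparison isolates it. The primary contrast is read at Month 18, six months after the second randomization, when half of the EF non-responders have already been assigned IF. A positive result could mean that immediate IF beats stepping up, or only that it beats never adding IF. The cost analysis has the same gap: unless cell C is assigned to a strategy, the cost of stepping up is not estimated.

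**Working it through.** **Inputs.** 40 randomized sites and 20 patients per site (Section V.C); both randomizations 1:1 (Section V.C), so about 20 sites start REP+EF. The plan's sample size reproduces: 40 × 20 = 800 patients.

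Let q be the share of REP+EF sites still non-responsive at Month 12. The plan does not state q. In the pilot (Section IV), three of four sites failed on REP and two more responded once EF was added. Counting two of those three gives q = 1/3; the pilot's own 50% gives q = 1/2. I take q = 3/4 as a pessimistic upper value. All three are assumptions.

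**1. What the pooled arm estimates.** Let A, B and C be the cell means.

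- Pooled mean = (1−q)A + (q/2)B + (q/2)C
- Strategy A+B = (1−q)A + qB
- Strategy A+C = (1−q)A + qC

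The average of the last two lines is the first, for every q. The equal weighting applies to strategy means, not to sites: responding sites (A) belong to both strategies, and only non-responders are split.

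**2. What B vs C covers.** Subtracting, (A+C) − (A+B) = q(C − B). Secondary Aim 1 therefore already addresses that pair, on the non-responder scale. The two comparisons with D+E are what is missing.

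**3. Why pooling hides the answer.** For illustration, let D+E exceed A+B by 1.22 MCS points. This is the earlier trial's coefficient in Section IV, which was against REP alone, not REP+EF. If A+C recovers a fraction f of that gain by Month 18, the pooled contrast is 1.22 × (1 − f/2) and the A+C contrast is 1.22 × (1 − f):

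| f | Pooled vs D+E | A+C vs D+E |
|---|---|---|
| 0 | 1.22 | 1.22 |
| 0.5 | 0.92 | 0.61 |
| 1 | 0.61 | 0 |

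With f = 1, stepping up equals starting with IF, yet the pooled contrast still favours starting with IF by 0.61.

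**4. Cost illustration.** Section IV reports $5,500 per site for IF over 12 months. If that applied once to every site given IF, the average IF cost per site would be $5,500 under D+E and q × 5,500 under A+C: about $1,830, $2,750 and $4,125 at q = 1/3, 1/2 and 3/4.

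**5. Precision of a weighted comparison.** Non-responders had a one-half chance of following either REP+EF-first strategy, while responders follow both. Weights are therefore 2 and 1. With 20(1−q) sites in A and 10q in each of B and C:

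- Effective sites = (A + 2B)² / (A + 4B), using site counts, = 20/(1+q)
- Standard-error ratio to the pooled contrast = √[(1/20 + 1/effective) / (2/20)]

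| q | Sites A / B / C | Effective sites | SE ratio |
|---|---|---|---|
| 1/3 | 13.3 / 3.3 / 3.3 | 15.0 | 1.08 |
| 1/2 | 10 / 5 / 5 | 13.3 | 1.12 |
| 3/4 | 5 / 7.5 / 7.5 | 11.4 | 1.17 |

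Without weights, non-responders would be 3.3/16.7 = 20%, 5/15 = 33% and 7.5/12.5 = 60% of A+C, instead of 33%, 50% and 75%. The plan proposes no such unweighted comparison; the figures only show why weights are needed.

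**The case against.** The strongest reply is that the plan does what its numbered aims ask. A+B+C vs D+E is an intent-to-treat test of the Primary Study Aim, and a pooled first-stage effect is a legitimate estimand. B vs C addresses whether sites that fail on EF benefit from adding IF. The mismatch is only with the broader goal sentence. All of that stands, and it is why the primary contrast should not change.

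A second reply is that point estimates for every strategy can be recovered from planned output: A+C equals the pooled mean plus (q/2)(C − B), and A+B equals it minus that amount. This also stands, up to differences between the two models. It gives no pre-specified joint estimate, and no standard error that accounts for both sources.

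A reader might infer more than the documents support:

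- **That no embedded strategies are compared.** B vs C compares two of the three, scaled by q.
- **That the pooled arm is a mixture no health system would use.** The documents do not address this. Each component strategy can be used as it stands, and responding sites are not split.
- **That the trial could establish stepping up as equivalent to immediate IF.** No margin is stated, and 11 to 15 effective sites give no basis for promising one.

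Finally, Figure 2 is not shown, and Section VI announces exploratory analyses although only the cost analysis is then labelled exploratory. This limits certainty about what else was intended, but no such comparison appears in the text.

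**Conclusion.** The concern holds as a gap between the overarching goal and the planned analyses, not as an error in the primary analysis. Missing are A+B vs D+E and A+C vs D+E, each with its own estimate and interval, on SF-12 MCS and on cost. In the illustration, a pooled difference of 0.61 points is compatible with no difference at all between stepping up and starting with IF.

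It would go too far to conclude that the planned contrasts say nothing about which strategy is best: together with the observed q they imply point estimates. What they lack is a direct, pre-specified estimate with a valid standard error.

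The conclusion rests on cell meanings inferred from Sections II, V and VI (A as REP+EF responders, B and C as non-responders continuing or adding IF, D and E as REP+EF/IF sites). The precision figures assume q from 1/3 to 3/4 and equal site variance. The change is worth making because it is cheap and serves the stated goal.

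**What to change.** Keep A+B+C vs D+E as primary and B vs C as Secondary Aim 1. Add to Section VI:

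- A secondary weighted-and-replicated longitudinal analysis of SF-12 MCS. Give weight 2 to REP+EF sites non-responsive at Month 12, weight 1 to REP+EF responding sites (replicated into both A+B and A+C), and weight 1 to D+E sites.
- Site-clustered robust standard errors with a small-sample correction, since the number of sites is small. Replicated records must stay within their own site cluster.
- A+B vs D+E and A+C vs D+E at Months 18 and 24, reported as estimates with confidence intervals and without an equivalence claim.
- The Secondary Aim 2 cost and cost-effectiveness analysis by the same three strategies, which also settles how cell C sites are classed.

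The cost is some extra analysis work; no sites, visits or data are added. The price in precision is a standard error about 8-17% larger than for the pooled contrast under the stated assumptions, so the analysis belongs beside the primary contrast rather than in its place.

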It often takes years if not decades to translate evidence-based practices (EBPs) into community-based settings. This research-to-practice gap is especially pronounced for psychosocial EBPs for mental disorders. Despite the availability of psychosocial EBPs, they are not getting into the hands of frontline providers in community-based practices and ultimately, improving care for persons with mental disorders. Implementation strategies, which are highly specified, operationalized approaches, involve educating and supporting frontline providers and clinical managers in promoting the use of EBPs. Notably, Replicating Effective Programs (REP) is a previously established implementation strategy that includes standardized EBP toolkits, training and limited technical assistance focused on supporting frontline providers in implementing EBPs in their care settings. REP is a low-intensity strategy with minimal costs from the site's and provider's perspective. However, more enhanced implementation strategies might be needed especially when sites and providers face competing demands or when the EBPs require additional support from higher-level organizational leadership. Hence, we enhanced REP to include **Facilitation**, a previously established implementation strategy that provides more personalized coaching to frontline providers and clinical managers in promoting the use of clinical EBPs in routine care that addresses site-level organizational barriers to EBP adoption. Specifically, there are two Facilitation roles: External and Internal Facilitators. External Facilitators (EFs) resided outside the clinic and provided technical expertise to providers in adapting EBPs. Internal Facilitators (IFs) resided within each site with designated time to support EBP implementation through day-to-day provider engagement. REP in combination with EF and IF (**REP+EF/IF**) versus standard REP alone when applied to implement LG improved patient outcomes, notably mental health quality of life. However, IF requires additional time from sites, and not all sites may need IF. Therefore, an adaptive implementation strategy approach is necessary, whereby the REP implementation may need to be augmented if sites are not responding (i.e., not adopting EBP). In contrast to simply measuring correlates of implementation non-response, adaptive implementation strategies are augmented, or stepped, in direct response to limited uptake of EBPs among specific sites based on circumstances that may not be observable at baseline.

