Life Goals (LG) description and operationalization: The evidence for Life Goals was described earlier. There are three stages to the Life Goals program: initial contact, group sessions, and follow-up contacts/referral (Table 2). First, upon creating a list of patients appropriate for LG, providers will review medical records and confirm eligibility (see above). The LG provider will make an initial call to the patient, and introduce the LG program and schedule group sessions. After the LG provider identifies 6-10 patients, he or she will initiate the first group session, and will hold cohorts of group sessions until enrolling 20 participants. Participants can make up sessions over the phone or in person if they are unable to make group sessions. In the sessions, the LG provider will encourage active discussions that progressively have participants identify triggers to the symptom or episode, develop an action plan for identifying warning signs of symptoms, and an activity plan for adopting a specific health behavior to mitigate symptoms and promote wellness. Participants will be given a workbook with exercises on behavior change goals, symptom assessments, and coping strategies. The LG provider will then contact the patient six times after the end of the group sessions on a weekly basis to review symptoms, behavior change, and any concerns the patient might have. LG providers will also track patients' mood symptoms and health behaviors using a registry. Once participants complete the LG program, a one-page summary of their current mood symptoms and health behavior changes will be routed to their primary care or mental health provider for treatment planning. As in previous studies, LG providers will be trained to inform providers immediately if patients have elevated symptoms or suicidal ideation. This is incorporated into the clinic's routine clinical care. Study staff (outside outcomes assessors) will complete outcomes assessments on up to 20 patients who are receiving Life Goals at the clinic in order to measure the program's reach over time.

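### The Month 6 non-response rule can keep low-uptake sites out of the randomisation because a few patients attended well, and it cannot be applied as written at Month 12; k=40 also does not match the expected yield (minor)

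*Combined protocol and SAP*

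**What the plan says.** Section V.C says its definition rests on the preliminary studies and sets non-response as "<10 patients receiving LG within six months of initiating REP and that patients received <75% group sessions". Sites meeting it are randomised 1:1 to REP+EF or REP+EF/IF. Six months later, "sites that are still non-responsive (based on the same criteria) will be randomized 1:1".

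Other sections bear on the same rule:

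- **II. Project Aims, purpose:** "the REP implementation may need to be augmented if sites are not responding (i.e., not adopting EBP".
- **II. Project Aims, Primary Study Aim:** "sites that do not exhibit response to REP alone after 6 months (e.g., <10 patients receiving LG". This is count only, and offered as an example.
- **IV. Preliminary Work:** the only non-response rule reported is fewer than 10 of 20 patients having at least one LG session within three months of training. It has no session-completion limb.
- **V.F, LG fidelity:** the likely source of the threshold. "Average patient completion of group sessions of" at least 75% is linked there to better mental health quality of life. The text does not say which patients are averaged and does not mention the site rule.
- **V.E, Life Goals description:** "Participants can make up sessions over the phone or in person if they are unable to make group sessions". Whether these count as group sessions for the rule is not stated.

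On numbers, V.C says "it is expected that after six months of REP at least two-thirds of sites will be non-responsive to REP", starts from 80 sites, and sets k=40. Section VI defines the intent-to-treat sample as the 40 sites (800 patients) randomised at Month 6.

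**The concern.** This rule selects the sites for the only randomised comparisons in the study. Its two limbs are joined by *and*, so failing either one makes a site a responder. Good attendance among very few patients could therefore take a site out of the randomisation, although the stated purpose is to step up support where the programme is not being adopted.

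Two people with the same logs could also classify a site differently, depending on the denominator they assume. The rule is used again at Month 12, where it selects the sites for the B versus C comparison, and there its time window no longer fits. A tailoring rule is part of the adaptive strategy under test. If it cannot be reproduced, others cannot apply the strategy.

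**Working it through.** **Inputs.** Count threshold 10 and session threshold 75% (V.C); 4 group sessions per patient (V.E Table 2; V.F); cohort of 20 patients per site (V.C); 80 sites, k=40 and at least two-thirds non-responsive (V.C).

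**Session limb.** With n recipients and S sessions attended in total, the recipient average is S/(4n) and the cohort average is S/(4 × 20) = S/80. Under *and*, a site is non-responsive (NR) only if n < 10 and the average is below 75%; otherwise it is a responder (R).

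| n | S | S/(4n) | Class, recipient average | S/80 | Class, cohort average | Class, count only |
|---|---|---|---|---|---|---|
| 0 | 0 | 0/0 | undefined | 0% | NR | NR |
| 1 | 3 | 3/4 = 75% | R | 3.75% | NR | NR |
| 7 | 20 | 20/28 = 71.4% | NR | 25% | NR | NR |
| 7 | 21 | 21/28 = 75% | R | 26.25% | NR | NR |
| 9 | 27 | 27/36 = 75% | R | 33.75% | NR | NR |
| 9 | 36 | 36/36 = 100% | R | 45% | NR | NR |
| 10 | 40 | 40/40 = 100% | R | 50% | R | R |

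Two things follow. On the recipient average, a single session (20 or 21 of 28) decides whether a 7-patient site is randomised. On the cohort average, the largest possible value with fewer than 10 recipients is 9 × 4/80 = 45%, so the limb is always met and the rule reduces to the patient count. The 75% limb therefore changes a classification only on the recipient reading, and there it works by removing low-uptake sites.

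**Month 12.** Suppose a site treats 7 patients by Month 6 and 5 more in Months 6-12. Counted cumulatively it has 7 + 5 = 12 and clears the count limb. Counted over Months 6-12 it has 5 and does not; if those 5 average 2 of 4 sessions (50%), the site is non-responsive on either denominator. Taken literally, the count stays at 7, because the six months from REP initiation have ended. With k=40 allocated 1:1, the REP+EF arm has 20 sites. B versus C then has at most 10 per cell, and each reclassified site is 1/20 = 5% of that arm.

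**Number of sites.** The plan's own product reproduces: 40 × 20 = 800. Its link to the expected non-response does not: 80 × 2/3 = 53.3, so at least 54 sites and 54 × 20 = 1,080 patients. Forty of 80 is 50%. The gap is 14 sites and 280 patients. V.C also gives 800 as the whole project's patient number, whereas the V. Methodology Overview and Section VI give 1,600 for all 80 sites.

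**The case against.** The best defence is that the wording already points to one reading. The nearest antecedent for the session limb is the patients receiving LG, V.F speaks of average completion, and the cohort reading makes the limb redundant. The sponsor might mean a small site with good attendance to count as responsive, and the complaint is then one of design preference. The first part stands: the recipient average is the most natural reading. The second does not dispose of the point. On that reading the rule departs from the purpose and the count-only criterion in the Project Aims, and from the preliminary rule that V.C claims as its basis.

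It is also fair to say that re-assessment at Month 12 is plainly intended, so the frozen count of 7 is not a serious candidate. The choice between cumulative and Months 6-12 counting remains open.

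A reader might infer several stronger points that the documents do not support:

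- *That the disputed case is routine*, because "After the LG provider identifies 6-10 patients, he or she will initiate the first group session". The same section has providers run further groups until 20 are enrolled, no uptake distribution is given, and a site with 10 recipients is outside the dispute.
- *That sites with 10 or more poorly attending patients are also in doubt.* This needs *and* to be read as *or*, or the two limbs to be merged into one per-patient count. The text says neither.
- *That zero-uptake sites would be left out.* The rule returns no value for them on the recipient average, but the Project Aims make the intent plain.
- *That the study will fall short of 40 sites.* If sites respond independently with two-thirds non-responsive, the chance of at least 40 of 80 is 0.999. Forty may be a minimum or an allowance for site loss (25% would turn 53.3 into 40), but the available text states neither.

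**Conclusion.** The point holds and should be fixed. On its most natural reading, the V.C rule classes any site with 1 to 9 recipients averaging at least 3 of 4 sessions as a responder, against the stated purpose and both count-only versions. On the cohort reading, the session limb has no effect. The Month 12 window is undefined.

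A reader might go further and infer bias in the comparison of A+B+C with D+E. That does not follow, because the Month 6 rule is applied before randomisation. The harm is to which sites are randomised, and so to the population the result describes, and to reproducibility. How many sites would be affected cannot be estimated from the documents. The figures of 10 sites per cell and 5% per site for B versus C assume that exactly 40 sites are randomised. The mismatch between k=40 and an expected 54 or more is a minor matter of explanation.

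**What to change.** Reconcile the Project Aims, Preliminary Work and Section V.C into one site-level rule under which good attendance among a few patients does not make a low-uptake site responsive. State:

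- how the two limbs combine;
- the patient denominator for the session limb, including the status of a site with no recipients;
- what counts as receiving LG, and whether make-up sessions count;
- the Month 12 counting window, cumulative or Months 6-12.

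In Section VI, define the intent-to-treat sample as all sites randomised at Month 6 instead of a fixed 40. In V.C, either restate the expected number as 54 or more sites (1,080 or more patients), or say that 40 is a planned minimum or a cap, with its basis and, for a cap, how sites are chosen. Label 800 as the patients at 40 randomised sites and 1,600 as the project total.

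The cost is wording only. The monthly monitoring forms (V.E, REP Step 3) and the per-patient encounter log (V.F) already collect what any of these rules would need. The downside is that some sites whose few patients attend well would receive facilitation. Facilitation workload rises beyond the 40-site figure only if more than 40 sites are randomised, which the current text already implies.
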